8.4 Inclusion/Exclusion Criteria

Inclusion and exclusion criteria deviations will be provided in a data listing by subject.

8.5 Demographic and Baseline Characteristics

Subject demographics at screening include gender; age; race and ethnicity; height; weight; BMI; and baseline disease severity (IPSS-R and IPSS overall score and sub-components), and ECOG Performance Status, MDS WHO classification [3].

Gender, ethnicity, race, and disease history will be summarized as the number and percentage (n, %) of subjects within each category for the total group. Denominators used in the calculation of percentages will be based on the number of subjects in the ITT population for the total group.

Age, weight, height and BMI will each be summarized as a continuous variable using descriptive statistics (n, mean, standard deviation, median, minimum, and maximum) for the total group.

Demographic characteristics will be provided in a data listing by subject.

8.6 Prior Therapies

8.6.1 Prior and Concomitant Transfusion Therapy

Prior and concomitant transfusion therapies will be summarized by product (fresh frozen plasma, packed RBCs, platelets, whole blood, plasma, other) and volume used for the total group.

Transfusion therapies will be reported in a data listing by subject.

8.6.2 Prior and Concomitant Stem Cell Transplant Therapy

Prior and concomitant stem cell transplant therapies will be summarized by type (autologous, allogenic, syngeneic, unknown, other) and units provided for the total group.

Stem cell transplants will be reported in a data listing by subject, including age, diagnosis, IPSS-R and IPSS score, best response obtained and number of cycles received for each transplanted subject.

8.6.3 Prior MDS Therapy

Prior MDS therapy will be summarized by therapy class and coded term for the total group.

Prior MDS therapy will be reported in a data listing by subject.

8.7 Medical History

Medical history (including smoking history but excluding prior MDS therapies) will be summarized for each medical history code with descriptive statistics for the total group. Denominators for calculating percentages will be based on the number of subjects in the analysis population for each dose cohort and overall.

A summary table of smoking assessment will be summarized with descriptive statistics for the total group. Under protocol amendment 2, smoking assessment was added at days 1, 15 and 22 of each cycle

and the end of treatment visit. Records recorded as “Not Done”, as the visit was prior to this addition, will not be included in the summary table.

A comprehensive data listing of medical history by subject will also be provided.

9 EFFICACY ANALYSIS

The ITT population will be used for summaries and analyses of efficacy described below unless otherwise stated. In addition, the primary efficacy will also be produced for the EE and PP populations. If the PP and ITT populations are identical, the PP tables will not be provided.

In this study, efficacy will be assessed by response to treatment with pracinostat and azacitidine. Response to treatment will be determined using the IWG criteria for MDS.

A summary of disease response will be provided using frequencies (counts and percentages). Denominators for calculating percentages will be based on the number of subjects in the ITT population.

Response to treatment will be provided in a data listing by subject.

9.1 Primary Endpoint Analysis

Overall response rate

The primary efficacy endpoint is overall response rate (ORR) defined as complete remission (CR) or partial remission (PR) per IWG criteria. The ORR and associated 95% confidence interval will be calculated using an exact binomial distribution approach for each of the ITT, EE and PP populations. For the PP population, the response rate will also be summarized by treatment schedule. In addition, a waterfall plot of the percentage change in blasts will be provided, and a forest plot of the ORR and corresponding 95% confidence intervals will be provided for each of the risk factors detailed in section 6.3.

If the ORR is shown to differ between the two treatment schedules, additional tables split by treatment schedule may be provided,

9.2 Secondary Endpoint Analysis

Rate of Discontinuation due to possibly safety reasons

For both stages, the rate of treatment discontinuation in the first 3 cycles of therapy due to possibly safety-related reasons will be used as a secondary endpoint to evaluate the safety and tolerability. The rate of subject discontinuation in the first 3 cycles and associated 95% confidence interval will be calculated using an exact binomial distribution approach.

Progressive disease and transplant are reasons to discontinuation related to efficacy, therefore these events will be excluded from the analysis. All the other reasons for treatment discontinuation will be considered as possibly safety-related, therefore will be included in the analysis as events.

9.2.1 Clinical Response

Clinical response rates will be based on the best response achieved by each patient in the following hierarchy:

CR -> PR -> Marrow CR -> SD -> PD

The response rate is based on confirmed response, the following rules will be taken into account:

If a patient has 2 CRs at least 28 days apart, best response is CR;

If a patient has at least 1 PR followed by 1 CR at least 28 days later, but no subsequent CR (ie the CR is not confirmed), best response is PR;

If a patient has 2 PRs at least 28 days apart, but no subsequent CRs, best response is PR;

If a patient has at least 1 Marrow CR followed by 1 CR or PR at least 28 days later, but no subsequent CR or PR (ie the CR/PR is not confirmed), best response is Marrow CR;

If a patient has 2 Marrow CRs at least 28 days apart, but no subsequent CRs or PR, best response is Marrow CR;

If a patient has 2 stable disease (SD) at least 28 days apart, but no subsequent PD, best response is SD.

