Proposed Modified International Working Group Response Criteria for Altering Natural History of MDS	
Category	Response Criteria (responses must last at least 28 days)
Complete remission	
Bone marrow: $\leq 5\%$ myeloblasts with normal maturation of all cell lines*
 
Persistent dysplasia will be noted*†
 
Peripheral blood‡
 
Hemoglobin ≥ 11 g/dL
 
Platelets $\geq 100 \times 10^9/L$
 
Neutrophils $\geq 1.0 \times 10^9/L$†
 
Blasts 0%

Partial remission	
All CR criteria if abnormal before treatment except:
 
Bone marrow blasts decreased by $\geq 50\%$ over pretreatment but still $> 5\%$
 
Cellularity and morphology not relevant

Marrow CR†	
Bone marrow: $\leq 5\%$ myeloblasts and decrease by $\geq 50\%$ over pretreatment†
 
Peripheral blood: if HI responses, they will be noted in addition to marrow CR†

Stable disease	Failure to achieve at least PR, but no evidence of progression for > 8 weeks
Failure	Death during treatment or disease progression characterized by worsening of cytopenias, increase in percentage of bone marrow blasts, or progression to a more advanced MDS FAB subtype than pretreatment
Relapse after CR or PR	
At least 1 of the following:
 
Return to pretreatment bone marrow blast percentage
 
Decrement of $\geq 50\%$ from maximum remission/response levels in granulocytes or platelets
 
Reduction in hemoglobin concentration by ≥ 1.5 g/dL or transfusion dependence

Cytogenetic response	
Complete: Disappearance of the chromosomal abnormality without appearance of new ones
 
Partial: At least 50% reduction of the chromosomal abnormality

Disease progression	
For patients with:
 
Less than 5% blasts: $\geq 50\%$ increase in blasts to $> 5\%$ blasts
 
5% – 10% blasts: $\geq 50\%$ increase to $> 10\%$ blasts
 
10% – 20% blasts: $\geq 50\%$ increase to $> 20\%$ blasts
 
20% – 30% blasts: $\geq 50\%$ increase to $> 30\%$ blasts
 
Any of the following:
 
At least 50% decrement from maximum remission/response in granulocytes or platelets
 
Reduction in hemoglobin by ≥ 2 g/dL
 
Transfusion dependence

Survival	
Endpoints:
 
Overall: death from any cause
 
Event free: failure or death from any cause
 
PFS: disease progression or death from MDS
 
DFS: time to relapse
 
Cause-specific death: death related to MDS

Reference: [Cheson 2006](#).

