2.3.2 Secondary Endpoints

The secondary efficacy endpoints are:

- Complete remission (CR) rate: proportion of subjects with confirmed CR (i.e. 2 CRs at least 28 days apart) per IWG criteria. CR is defined as:
 - Bone marrow: $\leq 5\%$ myeloblasts with normal maturation of all cell lines; persistent dysplasia will be noted.
 - Peripheral blood (in the absence of transfusions)
 - Hemoglobin ≥ 11 g/dL
 - Platelets $\geq 100 \times 10^9/L$
 - Neutrophils $\geq 1.0 \times 10^9/L$
 - Blasts 0%
- Overall hematologic improvement (HI) rate: proportion of subjects who demonstrate major hematologic improvement per IWG criteria, for at least one criterion. Only subjects with pre-treatment abnormal values will be considered for this evaluation at 8 weeks.
- Clinical benefit rate (CBR): proportion of subjects with confirmed CR, PR, Marrow CR, or HI. All subjects who achieve hematologic CR, PR, marrow CR (with or without HI), or HI without marrow CR per IWG will be considered responders. PR is defined as all of the CR criteria if abnormal before treatment except bone marrow blasts, which can be decreased by $\geq 50\%$ over pretreatment but still $> 5\%$, and cellularity and morphology are not relevant. Marrow CR is defined, only in patients with MDS with excess blasts, as:
 - Bone marrow: $\leq 5\%$ myeloblasts and decrease by $\geq 50\%$ over pretreatment
 - Peripheral blood: if HI responses, they will be noted in addition to marrow CR
- Relapse: after CR or PR, at least one of:
 - Return to pretreatment bone marrow blast percentage

- Decrement of $\geq 50\%$ from maximum remission/response levels in granulocytes or platelets
 - Reduction in hemoglobin concentration by ≥ 1.5 g/dL or transfusion dependence
- Cytogenetic complete response/remission rate: proportion of subjects with disappearance of the chromosomal abnormality without appearance of new ones, by cytogenetic assessment in the subset of subjects with abnormal cytogenetics at baseline.
- Duration of response (DOR) will be derived in 2 ways: for subjects who achieve CR or PR (primary), and for subjects who achieve CR, PR, marrow CR or HI: time from initial determination of response to time of disease progression or death on study, whichever occurs first. For subjects who are alive and have not experienced disease progression on study (prior to receiving subsequent/new treatment or stem cell transplant), duration of response will be censored at the day of last disease assessment.

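### SAP 9.2.1 lets a single unconfirmed PR confirm a marrow CR, although a PR has marrow blasts above 5% and a marrow CR requires 5% or less

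*SAP*

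**What the plan says.** SAP 9.2.1 ranks responses as "CR -> PR -> Marrow CR -> SD -> PD" and introduces its best-response rules with "The response rate is based on confirmed response, the following rules will be taken into account". Two rules lead to Marrow CR:

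- The first begins "If a patient has at least 1 Marrow CR followed by 1 CR or PR at least 28 days later" and applies when that CR or PR is not followed by another, so is itself unconfirmed.
- The second needs two marrow CRs at least 28 days apart, and applies only if no CR or PR comes afterwards.

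SAP 2.3.2 gives the definitions. Marrow CR requires at most 5% myeloblasts and a fall of at least 50% from pretreatment. For PR it says "PR is defined as all of the CR criteria if abnormal before treatment except bone marrow blasts, which can be decreased by" at least 50% from pretreatment while remaining above 5%. Protocol Appendix D has the same two marrow criteria and heads its response table with the condition that "responses must last at least 28 days".

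SAP 9.2.1.3 counts confirmed marrow CR in CBR. SAP 2.3.2 and 9.2.2.1 include marrow CR in the wider of the two duration-of-response (DOR) analyses (CR, PR, marrow CR or HI).

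**The concern.** Confirmation should show that the earlier response was still present. The SAP appears to assume that any category higher in the ranking confirms a lower one. That works when the later response is a CR, which also keeps marrow blasts at 5% or less. It fails when the later response is a PR. On blood counts a PR is better than a marrow CR, which has no blood-count requirement, but on the marrow criterion it is worse. Nothing else in either document requires the later assessment to show blasts of 5% or less.

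The best-response table can therefore report a confirmed Marrow CR on evidence that contradicts it, and the same subject can enter CBR and the wider DOR set under that label.

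**Working it through.** **1. Can one marrow meet both criteria?** Let b be the pretreatment blast percentage and x the later one (SAP 2.3.2; Protocol Appendix D).

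- Marrow CR: x ≤ 5 and x ≤ 0.5b.
- PR, marrow part: x > 5 and x ≤ 0.5b.

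The conditions x ≤ 5 and x > 5 exclude each other. A grid of b and x from 0 to 19.5% in steps of 0.5 gave 0 pairs meeting both. A PR after a marrow CR therefore means that blasts went from at most 5% back above 5%.

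**2. Who can follow this path?** PR needs 5 < x ≤ 0.5b, so b > 10. Protocol 4.2 excludes blasts of 20% or more, so the relevant baselines run from above 10% to below 20%. At b = 19.5% the PR window runs from just above 5% to 0.5 × 19.5 = 9.75%.

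**3. Example.** Baseline 16%, so half of baseline is 8%.

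- First marrow 4%: 4 ≤ 5 and 4 ≤ 8, a marrow CR.
- Second marrow at least 28 days later 7%, counts recovered: 7 > 5 and 7 ≤ 8, a PR.
- No later CR or PR: SAP 9.2.1 assigns best response Marrow CR.

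**4. Effect on CBR.** The documents give no expected CBR and no count of such subjects, so there is no planned figure to reproduce. The SAP names the exact binomial interval for CBR. As a check of that method, 24/60 gives a lower limit of 27.6%, as in SAP 4.2, and 9/40 gives 10.8% to 38.45%, against 10.8% to 38.4% in SAP 4.1.

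One subject changes CBR by 1/60 = 1.7 points. For illustration only, assume 36/60 responders and let k be the number who count solely because a PR confirmed a marrow CR:

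| k not counted | CBR | Exact 95% CI |
|---|---|---|
| 0 | 36/60 = 60.0% | 46.5 to 72.4 |
| 1 | 35/60 = 58.3% | 44.9 to 70.9 |
| 3 | 33/60 = 55.0% | 41.6 to 67.9 |
| 5 | 31/60 = 51.7% | 38.4 to 64.8 |

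**5. Effect on ORR.** None. ORR counts confirmed CR or PR, and a subject on this path has neither.

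**The case against.** The best defence is that the subject is in a category that counts toward CBR at both assessments. Blasts are down by at least 50% each time, and the PR also requires recovered blood counts. Some such subjects may enter CBR through HI anyway, if two HIs at least 8 weeks apart are recorded (SAP 9.2.1.2). This stands. It means that counting the subject as clinical benefit is not plainly wrong, but it does not rescue the label of confirmed Marrow CR.

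The path is also narrow. Protocol 5.2.4 schedules marrows at the end of Cycles 2 and 6 but says that, once a marrow CR is documented, the biopsy need not be repeated unless clinically indicated. This stands too, and the path is probably rare.

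A reader might infer more than the documents support:

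- *That the rise in blasts is disease progression.* In the example, 4% to 7% is a 75% increase to above 5%, which fits Appendix D's blast criterion if read from the on-treatment level. On that reading the second assessment is progression, not PR, and the rule is never triggered. Read from the 16% baseline, it is a PR. Both readings cannot be used at once.
- *That DOR is biased in a known direction.* DOR runs from first response to progression or death. If the rise is progression, the subject adds an early event. If it is a PR, the subject is still in a category that the wider DOR set counts. No direction is shown.
- *That the marrow CR lasted less than 28 days.* A later PR shows that the marrow CR had ended by then, not when it ended. The point is that it cannot serve as confirmation.

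**Conclusion.** The PR branch of the marrow CR rule in SAP 9.2.1 is wrong as written, because an assessment with blasts above 5% cannot confirm a response defined by blasts of 5% or less. This follows from the definitions and needs no assumption. What is certain is the mislabelling in the best-response summary.

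The effect on results is small and conditional: at most 1.7 points of CBR per affected subject at N = 60, only for subjects with baseline blasts above 10% who have a repeat marrow, and nil for any who qualify through HI. The figure takes 60 as the CBR denominator; the actual ITT, EE or PP count may differ. The frequency is not given in the documents. A reader might conclude that CBR is materially inflated; the documents do not support this, because they give no count of such subjects and each is in a CBR category at both assessments. This is a minor correction to a secondary endpoint.

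**What to change.** Change SAP 9.2.1 before the analysis:

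1. Let only a later marrow CR or CR, at least 28 days on, confirm a marrow CR, by deleting the words *or PR* from the confirming event.
2. Let two marrow CRs at least 28 days apart stand as Marrow CR whether or not an unconfirmed CR or PR follows. Without this, step 1 would leave two marrow CRs followed by one unconfirmed PR outside every response rule, because the two-marrow-CR rule now excludes any later CR or PR.
3. Add a rule for a marrow CR followed only by a single unconfirmed PR, which step 1 alone would leave unclassified. Report it as its own category, not as confirmed Marrow CR. State whether it counts in CBR and in the wider DOR set, and show CBR with and without these subjects.

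The cost is a few lines of SAP text, one more table line, and a CBR that may be slightly lower. No new data are needed.

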5.2 Study Treatment

Study visits should occur on a 28-day schedule. A -4 day to +7-day window is allowable for each clinic visit to accommodate subject request, holidays, weekends, inclement weather, or other unforeseen circumstances.

Pracinostat is to be taken in the morning on an empty stomach or following a light meal once a day on Days 1, 3, and 5 (Week 1); Days 8, 10, and 12 (Week 2); and Days 15, 17, and 19 (Week 3); with a week of rest during Week 4. Pracinostat will be administered in the clinic on Day 1 of Cycle 1, and subjects may self-administer at home on all other days. Pracinostat is to be taken before azacitidine. Missed doses of pracinostat should not be made up (refer to [Section 3.1.1](#)). To monitor pracinostat dosing, subjects will be given a dosing diary card to track medication compliance.

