A BMBx and aspirate to assess cellularity, blast percentage, morphology (dysplasia), and cytogenetics (if abnormal at baseline), as well as a CBC with differential will be required at the end of Cycles 2 and 6, with evidence of disease progression, with evidence of hematologic CR which may occur after Cycle 6, and prior to transplant if the subject becomes a candidate for transplant. Once a marrow CR is documented, there is no need to repeat a BMBx unless clinically indicated.

Ideally, transplant will be after the conclusion of ≥ 4 cycles of therapy. The following assessments are to be performed, and the Medical Monitor is to be advised of the results prior to discontinuing treatment for transplant:

- Bone marrow biopsy and aspiration (classic cytogenetics, fluorescence in-situ hybridization [FISH], and molecular studies, if done at baseline).*
- CBC with differential and blasts.

* FISH and molecular studies are not required by protocol, but results should be collected in the electronic data capture (EDC) system if performed as per local practice.

Transfusions in the 8 weeks prior to starting study drugs and while on study and hematopoietic growth factor use will also be captured to assess efficacy.

Local (i.e., Investigator) assessments of response will be utilized for the primary efficacy analyses, employing the IWG standardized response criteria for evaluating clinically significant responses in MDS ([Cheson 2006](#)). These criteria measure alterations in the natural history of disease, hematologic improvement, cytogenetic response, and improvement in health-related quality of life. Diagnosis of MDS according to the WHO classifications are presented in [Appendix B](#).

The IWG Response Criteria for MDS are presented in [Appendix D](#). The response categories are as follows:

- CR
- PR
- Marrow CR
- HI
- Stable Disease
- Failure
- Relapse after CR or PR
- Cytogenetic Response
- Disease Progression
- Survival

A CBC with differential will be required for confirmation of CR or PR 8 weeks following the initial report of response.

Modified IWG response criteria are presented in [Appendix D](#).

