9.2.1.3 Clinical Benefit rate (CBR)

Clinical benefit rate (CBR) will be defined as the proportion of subjects with confirmed CR, PR, marrow CR, or HI. All patients who achieve hematologic CR, PR, marrow CR (with or without HI), or HI without marrow CR per modified IWG response criteria will be considered responders. The response rate and associated 95% confidence interval will be calculated using an exact binomial distribution approach for the ITT, EE and PP populations. In addition, a forest plot of the ORR and corresponding 95% confidence intervals will be provided for each of the risk factors detailed in section 6.3.

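### SAP 9.2.1 relies on a second marrow that the protocol waives once marrow CR is documented, so subjects whose only benefit is marrow CR may be left out of the clinical benefit rate

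*SAP*

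**What the plan says.** SAP 9.2.1 opens its classification rules with "The response rate is based on confirmed response" and gives two routes to marrow CR as best response:

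- Route 1: "If a patient has 2 Marrow CRs at least 28 days apart, but no subsequent CRs or PR, best response is Marrow CR".
- Route 2 begins "If a patient has at least 1 Marrow CR followed by 1 CR or PR at least 28 days later" and applies when that CR or PR is not itself confirmed.

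SAP 9.2.1.3 defines the clinical benefit rate as the "proportion of subjects with confirmed CR, PR, marrow CR, or HI". The next sentence there treats everyone who achieves marrow CR, with or without HI, as a responder.

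Protocol 5.2.4 says a marrow "will be required at the end of Cycles 2 and 6, with evidence of disease progression", and also when hematologic CR appears and before transplant. The same paragraph adds: "Once a marrow CR is documented, there is no need to repeat a BMBx unless clinically indicated". Appendix A, footnote k, repeats this waiver. The one confirmation procedure in Protocol 5.2.4 is: "A CBC with differential will be required for confirmation of CR or PR 8 weeks following the initial report of response". It does not mention marrow CR.

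**The concern.** Marrow CR is defined by marrow blasts (Protocol Appendix D; SAP 2.3.2). Read naturally, a second marrow CR therefore needs a second marrow, and that is the procedure the protocol makes optional. Two subjects with the same course could be classed differently because one site repeated the biopsy and the other used the waiver.

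Three outputs are exposed:

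- CBR, a secondary endpoint with its own forest plot.
- The duration-of-response analysis over CR, PR, marrow CR or HI.
- The marrow CR row of the best-response table.

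CBR and response duration are secondary objectives of a study meant to inform a confirmatory trial, so an avoidable ambiguity in either is worth removing.

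**Working it through.** **The rules side by side**

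| Situation | Protocol | SAP 9.2.1 |
|---|---|---|
| Marrow CR at end of Cycle 2 | Cycle 6 marrow is listed as required, but the waiver applies | Needs a second marrow CR, or a later CR or PR |
| Marrow CR first seen at end of Cycle 6 | No later routine marrow; only event-driven ones | Same |
| One marrow CR with nothing after it | No confirmation step given | No rule given |

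Route 2 is narrow. PR requires marrow blasts still above 5%, whereas marrow CR requires 5% or less, so PR after marrow CR would be unusual. The CR branch helps only subjects whose blood counts later reach CR levels. The fallback to stable disease itself needs two such assessments at least 28 days apart, so a single marrow CR may end up unclassified.

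For CR the SAP does resolve the matter. Section 9.2.1.1 accepts one qualifying marrow and confirms on repeated peripheral blood. Nothing equivalent is written for marrow CR.

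**Timing**

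Protocol 5.2 states "Study visits should occur on a 28-day schedule", with a window of −4 to +7 days.

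- End of Cycle 2: 2 × 28 = Day 56. End of Cycle 6: 6 × 28 = Day 168.
- Gap: 168 − 56 = 112 days.
- Shortest: (168 − 4) − (56 + 7) = 101 days. Longest: (168 + 7) − (56 − 4) = 123 days.

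If the Cycle 6 marrow is taken, it meets the 28-day rule easily. If it is waived, no routine marrow can meet it.

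**Who is exposed**

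A subject leaves CBR only if all of these hold: one marrow CR; no later CR or PR; no confirmed HI; and no second marrow still showing marrow CR. SAP 2.3.2 also limits marrow CR to MDS with excess blasts. Subjects with marrow CR and confirmed HI stay in CBR, but they may be misplaced in the best-response table because HI is not in the SAP 9.2.1 hierarchy.

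**Size (illustration)**

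The documents give no expected CBR or marrow CR rate, so there is no stated figure to reproduce. As a method check, exact binomial 95% intervals match the plan's own numbers: 24/60 gives a lower bound of 27.6%, 9/40 gives 10.8–38.4%, and 18/40 gives 29.3–61.5%.

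Assume 36 of 60 subjects have clinical benefit when a single marrow CR counts. Let m be the number whose only benefit is marrow CR, and let k of them lack a second qualifying marrow. Then CBR = (36 − k)/60 and the loss is k/60.

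| m | k | Counted | CBR | Exact 95% CI | Loss (points) |
|---|---|---|---|---|---|
| any | 0 | 36/60 | 60.0% | 46.5–72.4 | 0 |
| 3 | 2 (half, rounded up) | 34/60 | 56.7% | 43.2–69.4 | 3.3 |
| 3 | 3 | 33/60 | 55.0% | 41.6–67.9 | 5.0 |
| 6 | 3 | 33/60 | 55.0% | 41.6–67.9 | 5.0 |
| 6 | 6 | 30/60 | 50.0% | 36.8–63.2 | 10.0 |
| 12 | 6 | 30/60 | 50.0% | 36.8–63.2 | 10.0 |
| 12 | 12 | 24/60 | 40.0% | 27.6–53.5 | 20.0 |

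ORR and the CR rate do not use marrow CR and do not move.

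**The case against.** A reader might infer that the protocol forbids the repeat marrow, that a subject managed per protocol can never satisfy the SAP, and that clinical benefit is therefore undercounted across the board. The documents do not support this. The waiver is permissive. A Cycle 6 marrow, or one taken at hematologic CR, before transplant or at certain end-of-treatment visits (Protocol 5.3), can still confirm. Route 2 exists, and subjects with confirmed CR, PR or HI remain in CBR regardless.

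Three further points deserve weight:

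- **A second biopsy is inferred.** The SAP asks for two marrow CRs, not two biopsies, and for CR it meets similar wording with one marrow plus blood counts. However, that provision is not extended to marrow CR, which is defined on marrow blasts.
- **The CBR text is ambiguous.** Protocol 9.3.1 and SAP 9.2.1.3 both ask for confirmed responses and then count everyone who achieves one. The duration-of-response text also speaks of achieving response. A single marrow CR could count on that reading. This makes the undercount uncertain, but it also means two programmers could produce different results.
- **A single marrow is not plainly the right standard.** The protocol's own CBR says confirmed, and Appendix D requires responses to last at least 28 days. Durability must therefore be kept in any revised rule.

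These points limit the claim but do not remove the gap.

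**Conclusion.** The inconsistency is real but limited. The SAP has no rule for one marrow CR without a later qualifying assessment, and the protocol neither requires the repeat marrow nor offers another way to confirm marrow CR. If the strict rule is applied, inclusion of marrow-CR-only subjects in CBR and the broader duration-of-response set depends partly on site biopsy practice. Relative to counting a single durable marrow CR, any error in CBR is downward.

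The size cannot be fixed from the documents. With 3 to 12 affected subjects out of 60 (assumed), the loss is 0 to 20 points. The upper end requires all 12 to have marrow CR as their only benefit and none to be re-sampled. The primary efficacy endpoint is untouched and all analyses are descriptive, so this is a contained correction to secondary endpoints that should be made before database lock.

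**What to change.** Reconcile SAP 9.2.1 and 9.2.1.3 with the protocol waiver before database lock:

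1. Count a single qualifying marrow CR when there is no evidence of progression for at least 28 days, judged on CBC with blasts and on any marrow that was done.
2. Apply that one rule to the best-response table, to CBR, and to the duration-of-response set covering CR, PR, marrow CR or HI.
3. Also report CBR under the strict two-marrow rule.

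The cost is SAP text and one additional CBR result. No extra procedures are needed, since Protocol 5.2.1 already collects a CBC with blasts on Day 1 of every cycle. The drawback is that blood counts can miss a rise in marrow blasts, so the single-marrow figure may overcount durable responses. Reporting the strict figure beside it makes that visible.
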